7.3 Exploratory Objectives (if applicable)

Exploratory Aim: To explore the effects of mavoglurant on alcohol responses, including stimulation, sedation, intoxication, and cognitive/motor performance.

8 Study Design

8.1 General Design Description

Double blind placebo-controlled trial of mavoglurant vs. placebo in light social drinkers (i.e., consuming 1- 6 standard alcoholic drinks per week and having engaged in at least one and no more than 12 binge drinking episodes in the past year). Participants will not meet criteria for a DSM-V Alcohol Use Disorder and must be willing to abstain from alcohol during the outpatient medication treatment phase. We propose to recruit 40 male and female social drinkers (to achieve a completer sample of 28 participants).

Subjects will sign informed consent and eligibility will be determined. Eligible subjects will participate in two alcohol administration lab sessions. They will be randomized to receive either 200 mg/day of mavoglurant or placebo for 7-10 days (14 in each study arm). During the outpatient medication administration phase, subjects will be observed daily as their medication is administered. Adverse events will be assessed. The first lab session will occur on Day 0 (prior to start of study medication) and the second lab session will occur following 7-10 days (as scheduling permits) of study medication. During each lab session, subjects will receive six successive doses of alcohol over a 90-min period designed to raise their blood alcohol levels to 80 mg/dl. Outcomes will include adverse events (during outpatient period and the lab session), safety labs (before and after drug and after alcohol), PK/PD of drug and alcohol, behavioral tests of cognition and body sway as well as self-reports of intoxication and other alcohol effects. Study staff will check in with subjects on the two days following the second lab session and an in-person follow up appointment will be scheduled 1 week after the second lab session.

8.1.1 Study Date Range and Duration

Subjects will participate in a screening visit and will complete lab session 1. Subjects will be seen daily, via video chat, to take their medication dose for the next 6 days (or up to 9 days, for scheduling reasons). On Day 7 (or up to day 10), they will come in for lab session 2 and take their final dose of medication. Subjects will then be followed up 1 week after the final lab session.

The enrollment period to accrue the 28 completing subjects is expected to be 6 years.

8.1.2 Number of Study Sites

One study site. Yale University will be the only site for this study

8.2 Primary Outcome Variables

The primary outcomes are clinical and laboratory measures including complete blood count and serum chemistries with calcium, magnesium, phosphate, liver function tests, B12 and TSH blood chemistries. We will also assess adverse events, heart rate, and blood pressure during the outpatient treatment period and during alcohol administration.

8.2.1 Secondary Outcome Variables (if applicable)

The secondary outcomes are blood alcohol levels on mavoglurant compared to no drug, and drug levels of mavoglurant before and after alcohol administration.

8.2.2 Exploratory Outcome Variables (if applicable)

Alcohol effects on stimulation, sedation, intoxication (Biphasic Alcohol Effects Scale), cognitive motor performance and physiological responses (blood pressure and heart rate) measured during the mavoglurant session and compared to responses measures during the baseline no-drug session.

8.3 Study Population

Participants will be social drinkers (consuming 1- 6 standard alcoholic drinks per week and having engaged in at least one and no more than 12 binge drinking episodes in the past year) who are not currently seeking treatment for their drinking behavior, and who are willing to abstain from drinking alcohol during the study, and who are between 21-50 years of age.

8.3.1 Number of Participants

We propose to recruit 40 male and female social drinkers (to achieve a completer sample of 28 participants). We anticipate having to consent approximately 90 subjects to reach these enrollment numbers.

8.3.2 Eligibility Criteria/Vulnerable Populations

All potential participants will be screened over the phone and if they appear to be eligible, will be brought in to be consented by a member of the research staff. A physical exam will be scheduled and reviewed by our Study Physician, and a psychological evaluation will be conducted by a trained clinical psychologist, or licensed social worker, to determine eligibility. In addition the participant's medical history may be verified from medical records by the study physician and study psychologist.

In order to be eligible to participate in this study, an individual must meet all of the following criteria:

- 1) Screened light social drinkers who are aged 21-50.
- 2) Able to read English at 6th grade level or higher and to complete study evaluations,
- 3) Consume 1- 6 standard alcoholic drinks per week, and has engaged in at least one and no more than 12 binge drinking episodes in the past year,
- 4) Willing to abstain from drinking alcohol during the outpatient study medication treatment period.
- 5) Fully vaccinated against COVID-19 (as defined by CDC guidelines)

An individual who meets any of the following criteria will be excluded from participation in this study:

- 1) Seeking treatment for alcohol drinking.
- 2) Current DSM-V abuse or dependence criteria for alcohol, dependence criteria for other substances, other than nicotine.
- 3) Positive test results at any appointments after the initial intake appointment on urine drug screens conducted for opiates, cocaine, marijuana, benzodiazepines and/or barbiturates.
- 4) Regular use of psychoactive drugs including anxiolytics and antidepressants.
- 5) Psychotic or otherwise severely psychiatrically disabled.
- 6) Any medical conditions (including hepatic and renal impairment) that would contraindicate the consumption of alcohol or administration of mavoglurant.
- 7) History of neurological trauma or disease, delirium, or hallucinations, or any significant systemic illness or unstable medical condition.
- 8) Women who are pregnant, nursing, or refuse to use a reliable method of birth control. Urine pregnancy tests will be completed at intake and prior to administration of alcohol
- 9) Subjects who report disliking spirits will be excluded because hard liquor will be provided during the alcohol administration.
- 10) Subjects who have taken any investigational drug and/or participated in another study which involves additive blood sampling and/or interventional measures that would be considered excessive in combination with the current protocol within 4 weeks immediately preceding admission to the treatment period.

APPROVED BY THE YALE UNIVERSITY IRB 11/22/2023

2000021703 Version 2.9

- 11) Subjects who report any daily drug use during the 30 days prior to randomization for the following: anxiolytics, beta blockers, central nervous system stimulants, hypnotics, non-therapeutic doses of neuroleptics and antidepressants, drugs with psychotropic activity or drugs which cause excessive sedation.
- 12) Subjects who have donated blood within the past six weeks.
- 13) Current use (within 30 days of screening) of specific psychoactive medications (e.g., typical neuroleptics, narcotic analgesics, antiparkinsonian medications, systemic corticosteroids, or medications with significant central anticholinergic activity, etc.)
- 14) Current use of warfarin.
- 15) Use of any medications that are contraindicated with mavoglurant and alcohol.
- 16) AST, ALT, total bilirubin >1.5 times upper normal; serum creatinine, >2 times upper normal limit, total bilirubin>1.5 times ULN; Serum creatinine >2.0 times ULN.

9 Methods

9.1 Treatment

9.1.1 Identity of Investigational Product

The study drug being used in this study is AFQ056 (Mavoglurant). Mavoglurant has not been approved for clinical use by the FDA. Mavoglurant oral tablets and matching placebo will be provided by Novartis.

9.1.2 Dosage, Administration, Schedule

Subjects will take 200mg of Mavoglurant each day (2 x 100mg modified release tabs or matching placebo) for 7-10 days. Study drug will be prepared and packaged by the Investigational Drug Services (IDS) at Yale-New Haven Hospital (YNHH). Any dose pausing or dose discontinuation will be decided by the PI and Study Physician.

9.1.3 Method of Assignment/Randomization

This is a double-blind, placebo-controlled study. The alcohol center biostatisticians ([name] and [name]) will create a randomization code list and forward it to the YNHH IDS pharmacy who will prepare the medication supply for each participant.

9.1.4 Blinding and Procedures for Unblinding

All staff and subjects will remain blind throughout the study. Only YNHH IDS and the study biostatisticians will have access to the blinding information. The PI will make the determination of if/when the blind needs to be broken.

9.1.5 Packaging/Labelling

Bulk supplies of the drug and placebo will be shipped from the company to the YNHH IDS in the form for 100 mg modified release tablets. The dose to be administered will be 200mg (two 100mg tablets) during the 7-10 day medication administration period. YNHH IDS will be responsible for monitoring drug supply and expiration.

Yale IDS will label all drug dispensed for this study.

9.1.6 Storage Conditions

Study drug will be received and stored under proper light/temperature conditions at YNHH IDS. Research staff will pick up the drug and dispense as appropriate to each subject. Expiration dates are observed, and drug will be dispensed accordingly. If drug needs to be returned, study staff will return to IDS and document appropriately. If called for by the study sponsor, the PI, and Novartis, IDS will destroy remaining study drug and provide documentation.

9.1.7 Concomitant therapy

Concomitant medications for each subject will be reviewed by the study physician prior to starting study medication. Warfarin use is not allowed. For all subjects, medications and illicit drugs that are forbidden during the study include opiates, cocaine, benzodiazepines and barbiturates. Regular use of psychoactive drugs, except for individuals on a stable dose of an antidepressant for at least 2 months. Also, any subjects who have taken any investigational drug within 4 weeks of the anticipated date of the first study dose.

9.1.8 Restrictions

Use of any illicit drugs is forbidden during study participation. Subjects are also asked not to come into the clinic for study appointments with a positive blood alcohol level (BAL). Since alcohol drinking is harmful to an unborn child, pregnant women may not participate in this study. As a result, the following precautions are necessary for female participants: 1) Repeated pregnancy test will be performed using a urine sample. A positive pregnancy test will result in them being excluded from the study, 2) females of childbearing potential must agree to use a reliable method of birth control during the study. Nursing mothers will also be excluded from the study.

9.2 Assessments

- a) Socio-demographic/General Information: At intake, demographic data, medical history and family psychiatric history will be assessed with interviews and self-report forms that provide data on age, race, socioeconomic status, marital status, educational and occupational levels, and significant medical history. These are adapted from previous diagnostic and clinical studies at this center. As of the restart of the continuation of this study May 2022 this assessment had several sections separated out into individual assessments. These are listed below: Time to 1st Cigarette (Fagerstrom ND), NIAAA alcohol questions on Alcohol Questions, SSADDA Risk/Protective Factors.
- b) SCID: The Structured Clinical Interview for DSM-V (SCID; First, et al., 1996) will be used to determine psychiatric diagnoses. This interview assesses DSM-V current and lifetime psychiatric diagnoses for anxiety, mood, psychotic, alcohol and substance use, somatoform, and eating disorders.
- c) Time-Line Follow-Back Assessment Method: (Sobell & Sobell, 1992). This interview procedure will be used to obtain quantity/frequency alcohol consumption data for each day during the 30-day period prior to the study, during the outpatient stabilization period, and during the one month follow-up ³³ Subjects are given a blank calendar covering the time interval to be re-constructed, and are asked to reconstruct retrospectively their drinking behavior over that interval. The process is facilitated by establishing anchor points (e.g., holidays, anniversaries, major national events, etc.). It can be scored to provide the number of days on which various levels of consumption occurred. The time-line method has good test-retest reliability and good validity for verifiable events. It has been used in numerous studies to compare pre- to post-treatment drinking.
- d) SAFTEE: (Levine & Schooler, 1986) This is a standardized form for collecting side effects and adverse events. The SAFTEE includes 1) open-ended questions about any changes in physical or health problems, appearance, or activity level, and 2) yes/no responses to a specific list of symptoms (which correspond to anticipated side effects associated with NRT) for a specified time. For each symptom reported on the SAFTEE a rater also records the date of onset, severity (minimal, mild, moderate, severe), whether it was drug-related, and action taken. The SAFTEE is administered at baseline and daily during medication appointments and again before and after each alcohol challenge. We will monitor the number of patients experiencing symptoms and the severity of symptoms.
- e) Biphasic Alcohol Effects Scale (Martin et al., 1993) This 14-item self-report, unipolar adjective rating scale will be used to measure the stimulant and sedative effects of alcohol during the two lab sessions. This instrument has been found to be sensitive to naltrexone's effects on alcohol intoxication.
- f) Drug Effects Questionnaire -5 (Morean et al., 2013) The DEQ-5 asks the individual to report how they feel and_five items: FEEL a drug effect, feel HIGH, DISLIKE the effects, LIKE the effects, and want MORE of the drug (in this case alcohol). Each item is assessed with a separate, unipolar 100mm visual analog scale rated from "not at all" to "extremely".

- g) Blood Alcohol Levels: Blood samples will be drawn to measure plasma levels of blood alcohol concentration (BAC) during the two lab sessions. Blood samples will be spun at room temperature and the serum will be stored at -4°C. Sample will be defrosted and analyzed using a clinical alcohol analyzer from Analox Instruments that uses a rapid high-performance alcohol analysis procedure using alcohol oxidase.
- h) Health Profile and Urinalysis: Chemistry and CBC Panels will be drawn at baseline, prior to the lab sessions, the morning following the lab sessions, and at follow-up. Urinalysis will also be done at these times. Additionally, a pregnancy test for females will be done at intake and prior to both lab sessions.
- i) Psychophysiological Measures: will include heart rate and blood pressure. The cuff of the Dinamap will be on subject's dominant arm since the IV will be placed in the non-dominant arm.
- j) Multi-Stage Decision Making Task (MSDM): The MSDM is a reinforcement learning paradigm that quantifies the degree to which subjects can integrate recent trial-to-trial information about a stimulus' likelihood of reward with acquired knowledge about whether some choices generally lead to disadvantageous outcomes vs. others that more often lead to reward. Each MSDM trial requires choices to be made in two stages. In the first MSDM stage, one's choice probabilistically leads to another set of choices. Then in the second stage, subjects learn that only some stimuli are likely to give rewards. Participants will get paid based on how much "treasure" they receive on the trials. Out of the 3 trials, they will be paid their highest score. So if the win treasure 10 times, then 15, then 12; they will receive \$15. Payments are expected to be \$20 or less.
- k) Concomitant Medications: A list of any other medications taken prior to the lab sessions, during the outpatient medication treatment period and through the follow-up will be kept for each subject indicating dosage, start date, end date, and indication. This will include all prescribed and over the counter medications.
- I) Plasma Mavoglurant (AFQ056) levels: Blood samples will be stored at -70°C and will be sent to Veeda Labs in India for analyses. The lab has a fully validated, FDA bioanalytical method available.
- m) Body Sway: will be measured using the Wii balance board (software developed by Nelson & Lim, University of Minnesota). Objective assessments of the effects of alcohol are an important supplement to measures of subjective response of alcohol effects. Traditional methods of assessing balance have been prohibitive based on complexity or cost. However, a novel software package developed by researchers at the University of Minnesota allows for a practical assessment of balance using the Nintendo Wii Fit Balance Board. With supervision, participants will simply stand on the board, which is very sensitive to weight distribution, for 30 seconds while data on their weight distribution patterns are collected.
- n) Yale Craving Scale (YCS; Rojewski et al., 2015): Labeled Magnitude Scale (gLMS), has been extended to measure hedonic ratings for foods, and we have adapted it for rating craving for tobacco and alcohol. It is not subject to the ceiling effects that often occur in craving research. We have been collecting craving data using this scale in our ongoing projects and the findings from this scale have been found to parallel those obtained using the Alcohol Urge questionnaire. A significant advantage of this scale is that following completion of baseline training to match perceived intensity of craving to the perceived brightness from the sun, each assessment timepoint only consists of a single visual analog scale of craving, making it very easy to administer.
- o) Quality of Drinks Rating Scale (QDRS): This assessment first asks the participant to rate a variety of alcoholic beverages on an 11-point Likert scale. The next two questions are write in questions "What is your favorite alcohol?" and What is your favorite alcohol drinks?" For the next two questions the participant selects their preferred alcohol drink for the study's

drinking session. The liquor is selected from a list of 5 options. Lastly the participant writes in their top three fruit juice mixers.

- p) Alcohol Effects Scale (AES): This 6-item questionnaire has the participant rate how they are feeling from the alcohol. There is a 10-item Likert scale ranging from 1 (Not at all) to 10 (extremely).
- q) Menstrual Cycle Data: Self-reports will be obtained from all women on their menstrual/gynecological status.
- r) Deary-Liewald reaction time task (Deary, et al., 2010): This computer task consists of two parts the Simple Response Time task (SRT) with just one stimulus, and when it appears, the participant needs to respond with the one response. Then there's the Choice Response Time task (CRT) that has multiple stimuli, and each stimulus requires a different response.
- s) Conners' Continuous Performance Test II (CPT II; Connors, 2000): This computer task involves the participant pressing the space bar or clicking the mouse button when a letter other than X shows up onscreen. Letters appear on the screen with different time intervals between each one. Exactly 14 minutes is required for completion.
- t) PROMIS Global Health: provide an assessment of a participant's individual assessment of his/her health (physical, emotional, and social), including an overall rating of pain
- u) Digits Backwards: from the Digit Span subtest of the Wechsler Adult Intelligence Scale (WAIS-IV) (29): as a legacy, objective measure of working memory, a factor associated with poor decision making in those with AUD.
- v) PROMIS Cognitive Function: will assess mental acuity, concentration, verbal and nonverbal memory, and verbal fluency and provide an assessment of a participant's perception of changes in cognitive abilities over the prior 4 weeks.
- w) Barrett Impulsivity Scale (BIS-11): is an 8-item trait measure of impulsiveness that yields two, 4-item subscales: (lack of) Self-Regulation ($\alpha = .75$) and Impulsive Behavior ($\alpha = .72$).
- x) Behavioral inhibition/activation system (BIS/BAS): is a 13-item measure that will be used to assess behavioral activation and behavioral inhibition, in response to rewards and punishment. We will use the Brief BIS/BAS, which has demonstrated scalar measurement invariance groups of interest (e.g., sex, age, race, education level, family history status, binge drinking status, and cigarette smoking status), as well as good convergent, discriminant, and predictive validity.
- y) UPPS Impulsive Behavior Scale (urgency subscales): evaluates the tendency to engage in impulsive drinking in response to negative and positive affect.
- z) Self-reported Habit Index (SRHI Alcohol): provides a self-report measure (6-item) of the degree to which alcohol drinking is habitual based on features of automaticity, lack of control and identity in human subject studies.
- aa) PROMIS Sleep and Impairment Measures: will measure past 7-day waking alertness, sleepiness, and impairment in function related to poor sleep because insomnia has been shown to be related to substance use and associated impairment.
- ab) AUDIT-C: a 3-item well-deployed quantity/frequency measure of alcohol use.
- ac) PROMIS Nicotine Dependence (ND): This 4-item scale will assess severity of nicotine dependence for cigarette smokers.
- ad) Time to 1st Cigarette (Fagerstrom ND): As a legacy measure of nicotine dependence, we will retain the item assessing time to the 1st cigarette of the day from the Fagerström Test of Nicotine Dependence

ae) NIAAA alcohol questions on Alcohol Questions: Longer-term drinking will be assessed with 6 questions recommended by the NIAAA Council's Task Force on Recommended Alcohol Questions, including past 12 months patterns of alcohol use and lifetime max drinks

af) SSADDA Risk/Protective Factors: Environmental Factors experienced prior to age 13 will be assessed with a brief module from the SSADDA that was developed by Drs. Gelernter and Kranzler in 2002 to assess major environmental risk and protective factors associated with AUD, based on data presented at a NIAAA sponsored gene x environment workshop meeting.

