9.2.1 Adverse Events Definition and Reporting

Adverse Events (AE) will be assessed from the time a subject starts the study through the final follow up appointment. The SAFTEE (see description above in section 6.2) will be used to assess any AE's at each visit. This procedure involves asking subject open-ended questions (e.g. How have you been feeling since your last visit) as well as reviewing a specific list of side-effects associated with the study medication and having the subject respond yes/no.

Definitions

Adverse event means any untoward medical occurrence associated with the use of an intervention in humans, whether or not considered intervention-related (21 CFR 312.32 (a)).

An AE or suspected adverse reaction is considered "serious" (SAE) if, in the view of either the investigator or sponsor, it results in any of the following outcomes:

- death.
- a life-threatening adverse event,
- inpatient hospitalization or prolongation of existing hospitalization,
- a persistent or significant incapacity or substantial disruption of the ability to conduct normal life functions,
- a congenital anomaly/birth defect, or
- An important medical event that may not result in death, be life-threatening, or require hospitalization may be considered serious when, based upon appropriate medical judgment, they may jeopardize the participant and may require medical or surgical intervention to prevent one of the outcomes listed in this definition. Examples of such medical events include allergic bronchospasm requiring intensive treatment in an emergency room or at home, blood dyscrasias or convulsions that do not result in inpatient hospitalization, or the development of drug dependency or drug abuse.

Severity

Adverse events will be graded according to [name grading scale, e.g. CTCAE v5.0]. For AEs not included in the protocol defined grading system, the following guidelines will be used to describe severity.

- Mild Events require minimal or no treatment and do not interfere with the participant's daily activities.
- Moderate Events result in a low level of inconvenience or concern with the therapeutic measures. Moderate events may cause some interference with functioning.
- Severe Events interrupt a participant's usual daily activity and may require systemic drug therapy or other treatment. Severe events are usually potentially life-threatening or incapacitating. Of note, the term "severe" does not necessarily equate to "serious".

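### The visible Lab Session 1 sheet omits the post-alcohol SAFTEE that section 9.2(d) requires, and the protocol's texts on the symptom list and causality grades do not agree

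*Combined protocol and SAP*

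**What the plan says.** Adverse events stand under the primary outcomes. Section 8.2 says: "We will also assess adverse events, heart rate, and blood pressure during the outpatient treatment period and during alcohol administration". Section 9.5.1 then tabulates them by severity and by relation to the intervention.

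The collecting instrument is the SAFTEE. Section 9.2(d) gives its timing: "The SAFTEE is administered at baseline and daily during medication appointments and again before and after each alcohol challenge". It also gives its use: "We will monitor the number of patients experiencing symptoms and the severity of symptoms". The form has open questions and a yes/no symptom list. Section 9.2(d) describes the items on that list with the words "which correspond to anticipated side effects associated with NRT". Section 9.2.1 describes the same procedure as "reviewing a specific list of side-effects associated with the study medication".

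The procedure sheet in section 11 is a timetable from 8:15 am to 6:00 pm. The SAFTEE appears in its 8:15 am block and nowhere else. The visit grid in 9.3.5 marks the SAFTEE once for each lab session and does not separate before from after.

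For causality, 9.2.1 defines five grades: Definitely, Probably, Potentially, Unlikely and Not Related. Section 9.5.1 names four labels: unlikely, possibly, probably and likely.

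**The concern.** A session sheet is what staff work from on the day. If it leaves out an assessment that the protocol text requires, the assessment is likely to be left out. Here the omission falls on solicited symptoms after alcohol at the session before any drug. Section 9.4.1 makes safe combined use a purpose of the study, and symptoms after alcohol alone are each participant's own reference for symptoms after alcohol plus drug. Without a same-day SAFTEE that reference depends on later recall.

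The two accounts of the symptom list matter because a yes/no list determines what is asked directly. NRT is not a treatment in this trial, whereas section 6.1.1 describes the dose-limiting events of mavoglurant as mainly hallucinations and other psychosis-like symptoms. The causality mismatch leaves one defined grade with no stated place in the primary tabulation.

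**Working it through.** The plan gives no figure to reproduce on this point. The check sets the texts side by side, with some clock arithmetic.

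**1. Which session the sheet covers.** It carries no session number. Two items place it at Session 1. Medication is handed over on the condition that the first dose falls on the next day. The baseline packet also holds scales, such as the AUDIT-C and SRHI, that the 9.3.5 grid marks for Lab Session 1 only. This is an inference from content, but a sound one.

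**2. SAFTEE administrations at Session 1.**
- Required by 9.2(d): one before and one after alcohol, so 2.
- On the sheet: 1, at 8:15 am. First drink at 12:00 pm; 12:00 − 8:15 = 3 h 45 min.
- Timed rows from 12:00 pm to 6:00 pm (6 h): no SAFTEE. They list YCS, AES and BAES ratings, body sway, CPT and reaction-time tasks, vital signs and alcohol levels.

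**3. Time to the next scheduled SAFTEE.** The sixth drink is served at 1:15 pm with 15 minutes to finish it, so drinking ends at 1:30 pm. Section 9.3 puts daily medication at about 10 am.
- From 1:30 pm on Day 0 to 10:00 am on Day 1: 10.5 h to midnight + 10 h = 20.5 h.
- From the first drink: 12 h + 10 h = 22 h.
- Section 9.3 allows a later first medication appointment. Each day of delay adds 24 h, so one day gives 44.5 h and 46 h. The 20.5 h and 22 h are therefore minimum values.

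**4. Symptom list.** One form cannot be described correctly both by "which correspond to anticipated side effects associated with NRT" and by "reviewing a specific list of side-effects associated with the study medication". The form itself is not in the documents, so the text does not show which description is right.

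**5. Causality, matched as generously as the text allows.**

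| Grade in 9.2.1 | Label in 9.5.1 |
|---|---|
| Definitely Related | likely (by position, not by name) |
| Probably Related | probably |
| Potentially Related | possibly (9.2.1 itself also speaks of possibly related events) |
| Unlikely to be related | unlikely |
| Not Related | none |

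One of the five grades has no label.

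**6. How many participants a collection change could still reach.** Section 7.2 mentions 10 and a further 14 completers: 10 + 14 = 24. The target is 28, so 28 − 24 = 4 remain. At the planned completion ratio of 28/40 = 0.70, 4 / 0.70 = 5.7, about 6 recruits. This assumes that the count in 7.2 is current and that the planning ratio holds for so few people.

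**7. Clerical items seen on the way.** The SAFTEE records "severity (minimal, mild, moderate, severe), whether it was drug-related, and action taken", but 9.5.1 has no place for the lowest of those four levels. The severity scale is an unfilled template: "Adverse events will be graded according to [name grading scale, e.g. CTCAE v5.0". With no scale named, the mild/moderate/severe fallback in effect covers every event, which agrees with 9.5.1. The pointer in "The SAFTEE (see description above in section 6.2) will be used" should lead to 9.2(d).

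**The case against.** The strongest reply is that little is lost. Section 9.2(d) sets no clock time for the second administration. The open question quoted in 9.2.1 asks about the time since the last visit, so the SAFTEE at the first medication appointment can reach back over the hours after drinking. On the day itself participants are supervised until their alcohol level falls or until about 6 pm, and they complete the AES repeatedly and the BAES twice after drinking starts. This stands as partial capture. It does not close the gap: AES and BAES rate alcohol effects and are not adverse-event forms, and recall after at least 20.5 h is weaker than an assessment tied to the session.

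It can also be said that no stated analysis changes. That is correct. Section 9.5.1 only tabulates adverse events; its between-session comparisons concern blood alcohol, chemistries, cell counts and urinalysis.

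A reader might infer four stronger things, none of which the documents support:
- That the SAFTEE is also missing after alcohol at Session 2. Section 9.3 refers to a procedure sheet for that session, but it is not visible, so nothing follows either way.
- That the drug-placebo comparison is damaged. The placebo arm receives alcohol without drug at Session 2, so that comparison remains. What is weakened is the within-person no-drug reference.
- That the wrong symptom list was used. The NRT phrase may be carried-over text, and the open questions apply in either case.
- That events graded *Not Related* will be dropped. Section 9.5.1 does not exclude them; it only gives them no label.

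Nor does much rest on correcting the labels while staff are blind: under 9.1.4 the study biostatisticians hold the blinding information in any case.

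**Conclusion.** The concern holds as a data-collection and consistency correction of minor weight. It is not a matter of analysis choice, and no sample size, error rate or stated between-arm analysis moves. The visible sheet schedules 1 of the 2 SAFTEE administrations that 9.2(d) requires at Session 1, and the missing one is the administration after alcohol. The two descriptions of the symptom list cannot both be right. One of five causality grades has no label in the primary tabulation.

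The conclusion rests on two assumptions: that the sheet is for Session 1, as its content indicates, and that 9.2(d) intends the post-alcohol SAFTEE to belong to the session, which is the natural reading but is not given as a time. The remaining reach of about 4 target completers depends on the count in 7.2 being current.

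**What to change.** - Add to the Session 1 sheet the post-drinking SAFTEE that 9.2(d) already requires, and check the Session 2 sheet for the same line.
- Reconcile 9.2(d) with 9.2.1 on the symptom list, and confirm which list is on the form in use.
- In 9.5.1, tabulate by the five causality grades of 9.2.1.
- Record the form version for each participant, and disclose any missing post-alcohol SAFTEE or list discrepancy for participants already completed.
- Clerical: name the severity scale or delete the placeholder, say how the lowest SAFTEE severity level maps to the three levels in 9.5.1, and correct the cross-reference.

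The cost is one line on a sheet, one phrase in 9.2(d), one label list in 9.5.1 and a few minutes per session. The collection change comes late and mixes form versions, with few participants left if 24 have completed. The wording, tabulation and disclosure changes need no new data and cover all participants.
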